7.6 CONSORT Flow Diagram

Enrolment Assessed for eligibility (n=) Excluded (n=) Not meeting inclusion criteria (n=) Declined to participate (n=) Other reasons (n=) **Allocation** Allocated to intervention (n=) • Received allocated intervention (n=) • Did not receive allocated intervention (give reasons) (n=) Follow-Up Lost to follow-up (give reasons) (n=) Discontinued intervention (give reasons) (n=) **Analysis**

• Excluded from analysis (give reasons) (n=)

Analysed (n=)

8. ADDITIONAL INFORMATION

8.1 Trial management group (TMG)

A Trial Management Group (TMG) will be established and Chaired by the CI. The TMG will have representation on it from the CTU and other investigators/collaborators who are involved in the study and provide trial specific expertise (e.g. trial statistician). This group will have responsibility for the day to day operational management of the trial, and regular meetings of the TMG will be held to discuss and monitor progress. The discussions of the TMG will be formally minuted and a record kept in the TMF.

A TMG Charter will be drawn up to detail the terms of reference of the TMG including roles and responsibilities. A Trial Steering Committee (TSC) will not be established for the trial and therefore the TMG will oversee the progress of the trial in terms of its organisation and accrual with the aim of steering it towards its overall objectives and will report to the Sponsor/Funder.

8.2 Data Monitoring and Ethics Committee (DMEC)

A DMEC will be appointed comprised of one diabetologist ([name]), two ophthalmologists with expertise on DR and DMO ([name] and [name]), and a Statistician ([name]) who is experienced in the analysis of clinical trials and will act as Chair for the DMEC. These members will be independent of the trial. A DMEC Charter will be drawn up to detail the terms of reference of the DMEC including roles and responsibilities. The DMEC's responsibility is to safeguard the interests of the trial participants, in particular with regard to safety, and to protect the validity and credibility of the trial. DMEC meetings will be formally minuted.

The inaugural meeting of the DMEC will take place prior to recruitment commencing. After recruitment commences the DMEC will review safety data at approximate 4 week intervals (with the first review commencing approximately 8 weeks after the first patient is recruited). The Chair of the DMEC will decide if these reviews raise any issues or concerns which require the DMEC to meet to discuss further. In addition, approximately every 3 months, the DMEC will review a full report on trial data (including outcome data, recruitment, pharmacovigilance and protocol deviations).

The DMEC will advise if in their view, the data arising from the study has provided 'proof beyond reasonable doubt' that for all, or some, the treatment should not be continued and standard treatment should be provided. Following a report from the DMEC, the CI will decide in consultation with the Sponsor what actions, if any, are required. Membership of the DMEC will include:

[name], (Chair), Associate Professor, Deputy Director of SITU, Centre for Statistics in Medicine, Nuffield Department of Orthopaedics, Rheumatology & Muscoloskeletal Sciences, University of Oxford, Botnar Research Centre, Nuffield Orthopaedic Centre, [name]

[name], Chair of Diabetes and Translational Research, Institute of Clinical Sciences; Block A, Queen's University Belfast, [name]

[name], Honorary Clinical Senior Lecturer, Institute of Genetic Medicine, Newcastle University

[name], Consultant Ophthalmologist, Moorfield Eye Hospital, [name]

Appendix 1: Summary Tables

Table 1. Baseline and Week 12 Characteristics

Characteristics		ARA290-DMO	Week 12
		n= <n></n>	n=(%)
Gender	Male	n(%)	-
	Female	n(%)	-
Study Eye	Left	n(%)	-
	Right	n(%)	-
Type of diabetes	Type 1	n(%)	-
	Type 2	n(%)	-
Age (years)		$xx.x \pm xx.x$	$xx.x \pm xx.x$
Weight (kg)		$xx.x \pm xx.x$	$xx.x \pm xx.x$
Height (m)		$xx.x \pm xx.x$	-
BMI (kg/m2)		$xx.x \pm xx.x$	-
Systolic Blood pressure (mm	Hg)	$xx.x \pm xx.x$	$xx.x \pm xx.x$
Diastolic Blood Pressure		$xx.x \pm xx.x$	$xx.x \pm xx.x$
Heart rate (bpm)		$xx.x \pm xx.x$	$xx.x \pm xx.x$
Temperature (degrees celsiu	ıs)	$xx.x \pm xx.x$	$xx.x \pm xx.x$
Oxygen saturation (%)		$xx.x \pm xx.x$	$xx.x \pm xx.x$
C peptide (ng/ml)		$xx.x \pm xx.x$	$xx.x \pm xx.x$
HbA1c (mmol/L)		$xx.x \pm xx.x$	$xx.x \pm xx.x$
Glucose (mmol/L)		$xx.x \pm xx.x$	$xx.x \pm xx.x$
HDL (mmol/L)		$xx.x \pm xx.x$	$xx.x \pm xx.x$
LDL (mmol/L)		$xx.x \pm xx.x$	$xx.x \pm xx.x$
Triglycerides (mmol/L)		$xx.x \pm xx.x$	$xx.x \pm xx.x$
Albumin Creatine Ratio		$xx.x \pm xx.x$	$xx.x \pm xx.x$
Liver Function Test	AST(mmol/L)	$xx.x \pm xx.x$	$xx.x \pm xx.x$
(LFT)	ALT(mmol/L)	$xx.x \pm xx.x$	$xx.x \pm xx.x$

Mean ±SD presented for continuous variables (or median [interquartile range] when appropriate) and no. (%) for all categorical variables.

Data listings for characteristics including co-morbidities and ophthalmologic condition will be included as an appendix in the final statistical report.

Table 2. Treatment after Trial Entry

Treatment after Trial Entry	ARA290-DMO
Treatment after Trial Entry	n = (%)
Study drug given	n(%)
Number of doses administered*	xx.x ± xx.x
Reasons for early termination of study drug	
Adverse Event	n(%)
Serious Adverse Event	n(%)
Protocol Deviation	n(%)
Other	n(%)
Protocol violations:	
Eligibility	n(%)
Study Drug Administration	n(%)
Visit out of schedule	n(%)
Other	n(%)

^{*}patients are expected to have received 120 doses over 120 days.

Table 3.1 Main Clinical Outcome variables

		Study Eye					Non-Study Eye						
		Base	line	Weel	k 12	Chang	je	Base	line	Weel	k 12	Cha	nge
		n =	(%)	n = ((%)	n = (°	%)	n =	(%)	n = ((%)	n =	(%)
•	tcome; best distance visual	· · · · · · · · · · · · · · · · · · ·		xx.x ± xx.x									
Central sub thickness (xx.x ± xx	.x	xx.x ± xx	.x	xx.x ± xx.x		xx.x ± xx	x	xx.x ± xx	.x	xx.x ± xx.x	
Central reti	inal sensitivity	xx.x ± xx	.x	xx.x ± xx	.x	xx.x ± xx.x		xx.x ± xx	.x	xx.x ± xx	.x	xx.x ± xx.x	
	Macular Ischaemia	Present Absent	n(%) n(%)	Present Absent	n(%) n(%)	Extension Reduction	n(%) n(%)	Present Absent	n(%) n(%)	Present Absent	n(%) n(%)	Extension Reduction	n(%) n(%)
		N/A	n(%)	N/A	n(%)	No change	n(%)	N/A	n(%)	N/A	n(%)	No change	n(%)
						N/A	n(%)					N/A	n(%)
	Foveal Ischaemia	Present Absent	n(%) n(%)	Present Absent	n(%) n(%)	Extension Reduction	n(%) n(%)	Present Absent	n(%) n(%)	Present Absent	n(%) n(%)	Extension Reduction	n(%) n(%)
Retinal		N/A	n(%)	N/A	n(%)	No change	n(%)	N/A	n(%)	N/A	n(%)	No change	n(%)
perfusion						N/A	n(%)					N/A	n(%)
	Peripheral Ischaemia	Present Absent	n(%) n(%)	Present Absent	n(%) n(%)	Extension Reduction	n(%) n(%)	Present Absent	n(%) n(%)	Present Absent	n(%) n(%)	Extension Reduction	n(%) n(%)
		N/A	n(%)	N/A	n(%)	No change	n(%)	N/A	n(%)	N/A	n(%)	No change	n(%)
						N/A	n(%)					N/A	n(%)
	Total area of	xx.x ± xx	.x	xx.x ± xx	.x	xx.x ± xx.x		xx.x ± xx	x	xx.x ± xx	.x	xx.x ± xx.x	•
Tear produ	ischaemia iction (mm)*	xx.x ± xx	X	xx.x ± xx	. X	xx.x ± xx.x		_		_		_	
Patient	EQ5d-5L	$xx.x \pm xx$		$xx.x \pm xx$		$XX.X \pm XX.X$		-		-		-	
reported	VFQ-25	$xx.x \pm xx$.x	$xx.x \pm xx$.x	$xx.x \pm xx.x$		-		-		-	

Northern Ireland Clinical Trials Unit

outcome scores C-SSR	xx.x ± xx.x	$xx.x \pm xx.x$	xx.x ± xx.x	-	-	-
% of participants with ≥ 10 ETDRS letter gain	· -	-	n(%)	-	-	n(%)
% of participants with ≥ 15 ETDRS letter gain		-	n(%)	-	-	n(%)

^{*}Study eye only

Mean ±SD presented for continuous variables (or median [interquartile range] when appropriate) and no. (%) for categorical variables.

Table 3.2 Descriptive Statistics for Serum for ARA 290 Antibodies

Status	Timepoint	Result	n =
Screening Status	Baseline	Negative	N (%)
		Potential Positive	N (%)
	Week 12	Negative	N (%)
		Potential Positive	N (%)
Confirmatory Status	Baseline	Not Applicable	N (%)
		Negative	N (%)
		Positive	N (%)
	Week 12	Not Applicable	N (%)
		Negative	N (%)
		Positive	N (%)

Table 3.3 Exploratory Analysis (Non-Study Eye subgroups)

		Non-Study Eye (Central subfield thickness <400 microns)				Non-Study Eye(Central subfield thickness ≥400 microns)							
		Baseline		Week 12 Change		је	Baseline		Week 12		Change		
		n = ((%)	n = ((%)	n = (°	%)	n = ((%)	n = ((%)	n =	(%)
Primary outcome; best corrected distance visual acuity		$xx.x \pm xx.x$ $xx.x \pm xx.x$.X	xx.x ± xx.x		xx.x ± xx.x		xx.x ± xx.x		xx.x ± xx.x		
Central sub thickness (xx.x ± xx.x		xx.x ± xx.x		xx.x ± xx.x		xx.x ± xx.x		xx.x ± xx.x		xx.x ± xx.x	
Central reti (dB)	nal sensitivity	xx.x ± xx.x		xx.x ± xx.x		xx.x ± xx.x		xx.x ± xx.x		xx.x ± xx.x		xx.x ± xx.x	
	Macular Ischaemia	Present Absent N/A	n(%) n(%) n(%)	Present Absent N/A	n(%) n(%) n(%)	Extension Reduction No change	n(%) n(%) n(%)	Present Absent N/A	n(%) n(%) n(%)	Present Absent N/A	n(%) n(%) n(%)	Extension Reduction No	n(%) n(%) n(%)
		ŕ				N/A	n(%)	ŕ				change N/A	n(%)
	Foveal Ischaemia	Present Absent	n(%) n(%)	Present Absent	n(%) n(%)	Extension Reduction	n(%) n(%)	Present Absent	n(%) n(%)	Present Absent	n(%) n(%)	Extension Reduction	n(%) n(%)
Retinal		N/A	n(%)	N/A	n(%)	No change	n(%)	N/A	n(%)	N/A	n(%)	No change	n(%)
perfusion						N/A	n(%)					N/A	n(%)
	Peripheral Ischameia	Present Absent	n(%) n(%)	Present Absent	n(%) n(%)	Extension Reduction	n(%) n(%)	Present Absent	n(%) n(%)	Present Absent	n(%) n(%)	Extension Reduction	n(%) n(%)
		N/A	n(%)	N/A	n(%)	No change	n(%)	N/A	n(%)	N/A	n(%)	No change	n(%)
						N/A	n(%)					N/A	n(%)
	Total area of ischaemia	xx.x ± xx	.x	xx.x ± xx	.x	xx.x ± xx.x		xx.x ± xx	.x	xx.x ± xx	.x	xx.x ± xx.x	
% of participants with ≥ 10 ETDRS letter gain		-		-		n(%)		-		-		n(%)	

Northern Ireland Clinical Trials Unit

% of participants with ≥			n(%)			n(%)
15 ETDRS letter gain	-	-	11(70)	-	-	11(70)

Mean ±SD presented for continuous variables (or median [interquartile range] when appropriate) and no. (%) for categorical variables.

Table 3.3 Exploratory Analysis (Non-Study Eye subgroups)

		Non-Study Eye (DMO Absent)					
		Baseline		Week	12	Chang	je
		n = (%)		n = (%)		n = (%)	
Primary outcome; best corrected distance visual acuity		xx.x ± xx.x		xx.x ± xx.x		xx.x ± xx.x	
Central sub thickness (r		xx.x ± xx.x		xx.x ± xx.x		xx.x ± xx.x	
Central retine (dB)	nal sensitivity	xx.x ± xx.	.x	xx.x ± xx.x		xx.x ± xx.x	
	Macular Ischaemia	Present Absent N/A	n(%) n(%) n(%)	Present Absent N/A	n(%) n(%) n(%)	Extension Reduction No change N/A	n(%) n(%) n(%) n(%)
Retinal perfusion	Foveal Ischaemia	Present Absent N/A	n(%) n(%) n(%)	Present Absent N/A	n(%) n(%) n(%)	Extension Reduction No change N/A	n(%) n(%) n(%) n(%)
	Peripheral Ischameia	Present Absent N/A	n(%) n(%) n(%)	Present Absent N/A	n(%) n(%) n(%)	Extension Reduction No change N/A	n(%) n(%) n(%) n(%)
	Total area of ischaemia	xx.x ± xx.x		xx.x ± xx.x		xx.x ± xx.x	
% of participants with ≥ 10 ETDRS letter gain		-		-		n(%)	
% of participants with ≥ 15 ETDRS letter gain		-			adian Fi	n(%)	

Mean ±SD presented for continuous variables (or median [interquartile range] when appropriate) and no. (%) for categorical variables.

Data listings for the visual outcomes will be included as an appendix in the final statistical report.

Table 3.4 Exploratory Analysis (All Eyes with DMO >400 Microns)

		All Eyes with DMO ≥ 400 Microns						
		Baseline		Week	(12	Chang	је	
		n = (%)		n = ((%)	n = (%)		
Primary outcome; best corrected distance visual acuity		xx.x ± xx.x		xx.x ± xx.x		xx.x ± xx.x		
Central sub thickness (r		xx.x ± xx	.x	xx.x ± xx.x		xx.x ± xx.x		
Central reti (dB)	nal sensitivity	xx.x ± xx	.x	xx.x ± xx.x		xx.x ± xx.x		
	Macular Ischaemia	Present Absent N/A	n(%) n(%) n(%)	Present Absent N/A	n(%) n(%) n(%)	Extension Reduction No change N/A	n(%) n(%) n(%) n(%)	
Retinal perfusion	Foveal Ischaemia	Present Absent N/A	n(%) n(%) n(%)	Present Absent N/A	n(%) n(%) n(%)	Extension Reduction No change N/A	n(%) n(%) n(%) n(%)	
	Peripheral Ischameia	Present Absent N/A	n(%) n(%) n(%)	Present Absent N/A	n(%) n(%) n(%)	Extension Reduction No change N/A	n(%) n(%) n(%) n(%)	
	Total area of ischaemia	xx.x ± xx.x		xx.x ± xx.x		xx.x ± xx.x		
% of participants with ≥ 10 ETDRS letter gain		-		-		n(%)		
% of partic	ipants with ≥ RS letter gain	-		-		n(%)		

Table 4.1 Safety Outcomes

		ARA290 n= <n></n>
AEs,	Total number of Adverse Events (AEs)	n
SAEs	Number of patients experiencing an AE	n (%)
and	Total number of Adverse Reactions (ARs)	n
SUSARs	Total number of Serious Adverse Events (SAEs)	n
	Number of patients experiencing an SAE	n (%)
	Total number of Serious Adverse Reactions (SARs)	n
	Total number of events related to study drug and unexpected (SUSARs)	n
	Total number of Deaths	n (%)
AE	General disorders and administration site conditions	n (%)
	Vascular disorders	n (%)
	Eye disorders	n (%)
	Gastrointestinal disorders	n (%)
	Psychiatric disorders	n (%)
	Metabolism and nutrition disorders	n (%)
	Infections and infestations	n (%)
	Nervous system disorders	n (%)
	Musculoskeletal and connective tissue disorders	n (%)
	Injury, poisoning and procedural complications	n (%)
	Respiratory, thoracic and mediastinal disorders	n (%)
	Skin and subcutaneous tissue disorders	n (%)
	Immune system disorders	n (%)
	Renal and urinary disorders	n (%)
	Cardiac disorders	n (%)
	Ear and labyrinth disorders	n (%)
	Investigations	n (%)
SAE	General disorders and administration site conditions	n (%)
	Vascular disorders	n (%)
	Eye disorders	n (%)
	Gastrointestinal disorders	n (%)
	Psychiatric disorders	n (%)
	Metabolism and nutrition disorders	n (%)
	Infections and infestations	n (%)
	Nervous system disorders	n (%)
	Musculoskeletal and connective tissue disorders	n (%)
	Injury, poisoning and procedural complications	n (%)
	Respiratory, thoracic and mediastinal disorders	n (%)
	Skin and subcutaneous tissue disorders	n (%)
	Immune system disorders	n (%)
	Renal and urinary disorders	n (%)
	Cardiac disorders	n (%)
	Ear and labyrinth disorders	n (%)
	Investigations	n (%)

Table 4.2 Adverse event summary of system organ class & preferred term

System Organ Class / Preferred Term	Total	Adverse Reaction (AR)	Unexpected Adverse Reaction (UAR)
Patients reporting at least one adverse event	n(%)	n(%)	n(%)
General disorders and administrative site conditions	n(%)	n(%)	n(%)
Head Cold	n(%)	n(%)	n(%)
Headache	n(%)	n(%)	n(%)
Flu Symptoms	n(%)	n(%)	n(%)
Non-cardiac Chest Pain	n(%)	n(%)	n(%)
Vascular disorders	n(%)	n(%)	n(%)
Hypertension	n(%)	n(%)	n(%)
Eye disorders	n(%)	n(%)	n(%)
Drop in visual acuity	n(%)	n(%)	n(%)
Flashing lights	n(%)	n(%)	n(%)
Gastrointestinal disorders	n(%)	n(%)	n(%)
Nausea	n(%)	n(%)	n(%)
Diarrhoea	n(%)	n(%)	n(%)
Vomiting	n(%)	n(%)	n(%)
Psychiatric disorders	n(%)	n(%)	n(%)
Insomnia	n(%)	n(%)	n(%)
Metabolism and nutrition disorders	n(%)	n(%)	n(%)
Hypertriglyceridemia	n(%)	n(%)	n(%)
Hyperglycemia	n(%)	n(%)	n(%)
Metabolism and nutrition disorders - other	n(%)	n(%)	n(%)
Infections and infestations	n(%)	n(%)	n(%)
Infections – 'Other'	n(%)	n(%)	n(%)
Skin and subcutaneous tissue disorders	n(%)	n(%)	n(%)
Facial Sunburn	n(%)	n(%)	n(%)
Investigations	n(%)	n(%)	n(%)
GGT Increased	n(%)	n(%)	n(%)
Abnormal blood test results	n(%)	n(%)	n(%)

Data listings for adverse events will be included as an appendix in the final statistical report.

Table 5. Exploratory Analysis – change from baseline to 12 weeks

Exploratory Analysis	Baseline	Week 12	Change
	n=(%)	n=(%)	n=(%)
Inflammatory Markers *			
Adenosine Deaminase (ADA)	$xx.x \pm xx.x$	$xx.x \pm xx.x$	$xx.x \pm xx.x$
Artemin (ARTN)	$xx.x \pm xx.x$	$xx.x \pm xx.x$	$xx.x \pm xx.x$
Axin-1 (AXIN1)	$xx.x \pm xx.x$	$xx.x \pm xx.x$	$xx.x \pm xx.x$
Beta-nerve growth factor (BDNF)	$xx.x \pm xx.x$	$xx.x \pm xx.x$	$xx.x \pm xx.x$
Caspase 8 (CASP-8)	$xx.x \pm xx.x$	$xx.x \pm xx.x$	$xx.x \pm xx.x$
C-C motif chemokine 4 (CCL4)	$xx.x \pm xx.x$	$xx.x \pm xx.x$	$xx.x \pm xx.x$
C-C motif chemokine 19 (CCL19)	$xx.x \pm xx.x$	$xx.x \pm xx.x$	$xx.x \pm xx.x$
C-C motif chemokine 20 (CCL20)	$xx.x \pm xx.x$	$xx.x \pm xx.x$	$xx.x \pm xx.x$
C-C motif chemokine 25 (CCL25)	$xx.x \pm xx.x$	$xx.x \pm xx.x$	$xx.x \pm xx.x$
C-C motif chemokine 28 (CCL28)	$xx.x \pm xx.x$	$xx.x \pm xx.x$	$xx.x \pm xx.x$
CD40L receptor (CD40)	$xx.x \pm xx.x$	$xx.x \pm xx.x$	$xx.x \pm xx.x$
CUB domain-containing protein 1 (CDCP1)	$xx.x \pm xx.x$	$xx.x \pm xx.x$	$xx.x \pm xx.x$
C-X-C motif chemokine 1 (CXCL1)	$xx.x \pm xx.x$	$xx.x \pm xx.x$	$xx.x \pm xx.x$
C-X-C motif chemokine 5 (CXCL5)	$xx.x \pm xx.x$	$xx.x \pm xx.x$	$xx.x \pm xx.x$
C-X-C motif chemokine 6 (CXCL6)	$xx.x \pm xx.x$	$xx.x \pm xx.x$	$xx.x \pm xx.x$
C-X-C motif chemokine 9 (CXCL9)	$xx.x \pm xx.x$	$xx.x \pm xx.x$	$xx.x \pm xx.x$
C-X-C motif chemokine 10 (CXCL10)	$xx.x \pm xx.x$	$xx.x \pm xx.x$	$xx.x \pm xx.x$
C-X-C motif chemokine 11 (CXCL11)	$xx.x \pm xx.x$	$xx.x \pm xx.x$	$xx.x \pm xx.x$
Cystatin D (CST5)	$xx.x \pm xx.x$	$xx.x \pm xx.x$	$xx.x \pm xx.x$
Delta and Notch-like epidermal growth factor-	$xx.x \pm xx.x$	$xx.x \pm xx.x$	$xx.x \pm xx.x$
related recep (DNER)			
Eotaxin-1 (CCL11)	$xx.x \pm xx.x$	$xx.x \pm xx.x$	$xx.x \pm xx.x$
Eukaryotic translation initiation factor 4E-	$xx.x \pm xx.x$	$xx.x \pm xx.x$	$xx.x \pm xx.x$
binding protein 1 (4E-BP1)			
Fibroblast growth factor 5 (FGF-5)	$xx.x \pm xx.x$	$xx.x \pm xx.x$	$xx.x \pm xx.x$
Fibroblast growth factor 19 (FGF-19)	$xx.x \pm xx.x$	$xx.x \pm xx.x$	$xx.x \pm xx.x$
Fibroblast growth factor 21 (FGF-21)	$xx.x \pm xx.x$	$xx.x \pm xx.x$	$xx.x \pm xx.x$
Fibroblast growth factor 23 (FGF-23)	$xx.x \pm xx.x$	$xx.x \pm xx.x$	$xx.x \pm xx.x$
Fms-related tyrosine kinase 3 ligand (Flt3L)	$xx.x \pm xx.x$	$xx.x \pm xx.x$	$xx.x \pm xx.x$
Fractalkine (CX3CL1)	$xx.x \pm xx.x$	$xx.x \pm xx.x$	$xx.x \pm xx.x$
Glial cell line-derived neurotrophic factor (hGDNF)	$xx.x \pm xx.x$	xx.x ± xx.x	xx.x ± xx.x
Hepatocyte growth factor (HGF)	$xx.x \pm xx.x$	$xx.x \pm xx.x$	$xx.x \pm xx.x$
Interferon gamma (IFN-gamma)	$xx.x \pm xx.x$	$xx.x \pm xx.x$	$xx.x \pm xx.x$
Interleukin-1 alpha (IL-1 alpha)	$xx.x \pm xx.x$	$xx.x \pm xx.x$	$xx.x \pm xx.x$
Interleukin-2 (IL-2)	$xx.x \pm xx.x$	$xx.x \pm xx.x$	$xx.x \pm xx.x$
Interleukin-2 receptor subunit beta (IL-2RB)	$xx.x \pm xx.x$	$xx.x \pm xx.x$	$xx.x \pm xx.x$
Interleukin-4 (IL-4)	$xx.x \pm xx.x$	$xx.x \pm xx.x$	$xx.x \pm xx.x$
Interleukin-5 (IL-5)	$xx.x \pm xx.x$	$xx.x \pm xx.x$	$xx.x \pm xx.x$
Interleukin-6 (IL-6)	$xx.x \pm xx.x$	$xx.x \pm xx.x$	$xx.x \pm xx.x$
Interleukin-7 (IL-7)	$xx.x \pm xx.x$	$xx.x \pm xx.x$	$xx.x \pm xx.x$
Interleukin-8 (IL-8)	$xx.x \pm xx.x$	$xx.x \pm xx.x$	$xx.x \pm xx.x$
Interleukin-10 (IL-10)	$xx.x \pm xx.x$	$xx.x \pm xx.x$	$xx.x \pm xx.x$
Interleukin-10 receptor subunit alpha (IL-10RA)	$xx.x \pm xx.x$	$xx.x \pm xx.x$	$xx.x \pm xx.x$
Interleukin-10 receptor subunit beta (IL-10RB)	$xx.x \pm xx.x$	$xx.x \pm xx.x$	$xx.x \pm xx.x$
Interleukin-12 subunit beta (IL-12B)	$xx.x \pm xx.x$	$xx.x \pm xx.x$	$xx.x \pm xx.x$
Interleukin-13 (IL-13)	$xx.x \pm xx.x$	$xx.x \pm xx.x$	$xx.x \pm xx.x$
interleukin-15 receptor subunit alpha (IL-15RA)	$xx.x \pm xx.x$	$xx.x \pm xx.x$	$xx.x \pm xx.x$
Interleukin-17A (IL-17A)	$xx.x \pm xx.x$	$xx.x \pm xx.x$	$xx.x \pm xx.x$
Interleukin-17C (IL-17C)	$xx.x \pm xx.x$	$xx.x \pm xx.x$	$xx.x \pm xx.x$
Interleukin-20 (IL-20)	$xx.x \pm xx.x$	$xx.x \pm xx.x$	$xx.x \pm xx.x$
Interleukin-20 receptor subunit alpha (IL-20RA)	$xx.x \pm xx.x$	$xx.x \pm xx.x$	$xx.x \pm xx.x$

Interleukin-22 receptor subunit alpha-1 (IL-22	$xx.x \pm xx.x$	$xx.x \pm xx.x$	$xx.x \pm xx.x$
RA1)	XX.X = XX.X	XX.X ± XX.X	XX.X ± XX.X
Interleukin-23 (IL-24)	xx.x ± xx.x	$xx.x \pm xx.x$	xx.x ± xx.x
Interleukin-33 (IL-33)	xx.x ± xx.x	$XX.X \pm XX.X$ $XX.X \pm XX.X$	xx.x ± xx.x
Latency-associated peptide transforming growth	xx.x ± xx.x	XX.X ± XX.X	xx.x ± xx.x
factor beta 1 (LAP TGF-beta-1)	XX.X = XX.X	XX.X ± XX.X	XX.X ± XX.X
Leukemia inhibitory factor receptor (LIF-R)	$xx.x \pm xx.x$	$xx.x \pm xx.x$	xx.x ± xx.x
Macrophage colony-stimulating factor 1 (CSF-1)	xx.x ± xx.x	$XX.X \pm XX.X$ $XX.X \pm XX.X$	xx.x ± xx.x
Macrophage inflammatory protein 1-alpha (MIP-	xx.x ± xx.x	XX.X ± XX.X	xx.x ± xx.x
1 alpha)	*****	*****	**** * ****
Matrix metalloproteinase-1 (MMP-1)	$xx.x \pm xx.x$	$xx.x \pm xx.x$	$xx.x \pm xx.x$
Matrix metalloproteinase-10 (MMP-10)	$xx.x \pm xx.x$	$xx.x \pm xx.x$	$xx.x \pm xx.x$
Monocyte chemotactic protein 1 (MCP-1)	$xx.x \pm xx.x$	$xx.x \pm xx.x$	$xx.x \pm xx.x$
Monocyte chemotactic protein 2 (MCP-2)	$xx.x \pm xx.x$	$xx.x \pm xx.x$	$xx.x \pm xx.x$
Monocyte chemotactic protein 3 (MCP-3)	$xx.x \pm xx.x$	$xx.x \pm xx.x$	$xx.x \pm xx.x$
Monocyte chemotactic protein 4 (MCP-4)	$xx.x \pm xx.x$	$xx.x \pm xx.x$	$xx.x \pm xx.x$
Natural killer cell receptor 2B4 (CD244)	$xx.x \pm xx.x$	$xx.x \pm xx.x$	$xx.x \pm xx.x$
Neurotrophin-3 (NT-3)	$xx.x \pm xx.x$	$xx.x \pm xx.x$	$xx.x \pm xx.x$
Neurturin (NRTN)	$xx.x \pm xx.x$	$xx.x \pm xx.x$	$xx.x \pm xx.x$
Oncostatin-M (OSM)	$xx.x \pm xx.x$	$xx.x \pm xx.x$	$xx.x \pm xx.x$
Osteoprotegerin (OPG)	$xx.x \pm xx.x$	$xx.x \pm xx.x$	$xx.x \pm xx.x$
Programmed cell death 1 ligand 1 (PD-L1)	$xx.x \pm xx.x$	$xx.x \pm xx.x$	$xx.x \pm xx.x$
Protein S100-A12 (EN-RAGE)	$xx.x \pm xx.x$	$xx.x \pm xx.x$	$xx.x \pm xx.x$
Signaling lymphocytic activation molecule	$xx.x \pm xx.x$	$xx.x \pm xx.x$	$xx.x \pm xx.x$
(SLAMF1)			XX.X = XX.X
SIR2-like protein 2 (SIRT2)	$xx.x \pm xx.x$	$xx.x \pm xx.x$	$xx.x \pm xx.x$
STAM-binding protein (STAMPB)	$xx.x \pm xx.x$	$xx.x \pm xx.x$	$xx.x \pm xx.x$
Stem cell factor (SCF)	$xx.x \pm xx.x$	$xx.x \pm xx.x$	$xx.x \pm xx.x$
Sulfotransferase 1A1 (ST1A1)	$xx.x \pm xx.x$	$xx.x \pm xx.x$	$xx.x \pm xx.x$
T-cell surface glycoprotein CD5 (CD5)	$xx.x \pm xx.x$	$xx.x \pm xx.x$	$xx.x \pm xx.x$
T cell surface glycoprotein CD6 isoform (CD6)	$xx.x \pm xx.x$	$xx.x \pm xx.x$	$xx.x \pm xx.x$
Thymic stromal lymphopoietin (TSLP)	$xx.x \pm xx.x$	$xx.x \pm xx.x$	$xx.x \pm xx.x$
TNF-beta (TNFB)	$xx.x \pm xx.x$	$xx.x \pm xx.x$	$xx.x \pm xx.x$
TNF-related activation-induced cytokine	$xx.x \pm xx.x$	$xx.x \pm xx.x$	$xx.x \pm xx.x$
(TRANCE)			
TNF-related apoptosis-inducing ligand (TRAIL)	$xx.x \pm xx.x$	$xx.x \pm xx.x$	$xx.x \pm xx.x$
Transforming growth factor alpha (TGF-alpha)	$xx.x \pm xx.x$	$xx.x \pm xx.x$	$xx.x \pm xx.x$
Tumor necrosis factor (ligand) superfamily,	$xx.x \pm xx.x$	$xx.x \pm xx.x$	$xx.x \pm xx.x$
member 12 (TWEAK)			
Tumor necrosis factor (TNF)	$xx.x \pm xx.x$	$xx.x \pm xx.x$	$xx.x \pm xx.x$
Tumor necrosis factor ligand superfamily	$xx.x \pm xx.x$	$xx.x \pm xx.x$	$xx.x \pm xx.x$
member 14 (TNFSF14)			
Tumor necrosis factor ligand superfamily	$xx.x \pm xx.x$	$xx.x \pm xx.x$	$xx.x \pm xx.x$
member 9 (TNFSF9)			
Urokinase-type plasminogen activator (uPA)	$xx.x \pm xx.x$	$xx.x \pm xx.x$	$xx.x \pm xx.x$
Vascular endothelial growth factor A (VEGF-A)	$xx.x \pm xx.x$	$xx.x \pm xx.x$	$xx.x \pm xx.x$
Carbamylated Albumin	$xx.x \pm xx.x$	$xx.x \pm xx.x$	$xx.x \pm xx.x$
Glycosylated Albumin	$xx.x \pm xx.x$	$xx.x \pm xx.x$	$xx.x \pm xx.x$
HbA1c (mmol/L)	$xx.x \pm xx.x$	$xx.x \pm xx.x$	$xx.x \pm xx.x$
*ng/ml	7717 - 7717	\(\lambda\) \(\lambda\) \(\lambda\) \(\lambda\)	$\lambda \lambda i \lambda - \lambda \lambda i \lambda$

^{*}pg/mL

Mean ±SD presented (or median [interquartile range] when appropriate)

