Similarly, the first in human studies comprising intravenous administration of a single ascending dose and multiple ascending dose in healthy volunteers, single intravenous and subcutaneous cross-over study in healthy volunteers and in subjects with renal impairment, and intravenous repeat dose in end-stage renal disease subjects undergoing haemodyalisis raised no safety concerns. Furthermore, studies using intravenous and subcutaneous administration of ARA 290 to patients with sarcoidosis [19, 20] and type 2 diabetes mellitus [21], including studies using the same dose and route as that proposed in the current study (4 mg subcutaneous administration of ARA 290), as well as studies in patients with critical limb ischaemia, and rheumatoid arthritis have supported further the safety profile of ARA 290. No allergic reactions have been observed to ARA 290.

Specifically, two studies have been previously conducted in people with type 2 diabetes mellitus, pre-diabetes and/or drug-naïve type 2 diabetes. In both, a daily subcutaneous 4 mg dose of ARA 290 administered during a 4 week period was used. In these studies 24 and 12 patients, respectively, received ARA 290 (24 and 12 received placebo, respectively). At the dosage used, ARA 290 appeared to be safe. Adverse events were generally mild; the most common being gastrointestinal issues, sleep disturbance and headache; the frequency of adverse events was similar in both ARA 290 and placebo groups.

The dose and route of 4 mg was chosen for the current study as pharmacokinetic studies using ARA 290 demonstrated that a daily subcutaneous dose of 4 or 6 mg of ARA 290 resulted in consistent blood levels above 1-2 nM, the minimum projected exposure for efficacy [18]. The current phase 2 study however, entails for the first time prolonging the duration of treatment, from 28 days, as used in most previous studies, to 84 days. The three month duration of the ARA 290 dosage was chosen as it is expected that if treatment were to be beneficial, functional and anatomical improvements could potentially be detected in this time period but may not be seen earlier, as only patients with severe DMO (central retinal thickness of \geq 400 microns) will be included in this investigation. Furthermore, it is unlikely that a detrimental effect on vision will be observed by postponing anti-VEGF treatment for this length of time [22]

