9.2 Study Drug Supply

As described in the IMPD, Patheon Italia S.P.A. [name] and PCI, [name] are responsible for manufacture, QP release, import and shipment of ARA290.

Study drug packs will be packaged and labelled by Victoria Pharmaceuticals, [name] in compliance with applicable regulatory requirements.

Study drug packs will be dispatched to the responsible pharmacist at the participating site under the instruction of the Trial Manager.

Each patient will be given an initial pack containing 30 vials of study drug. Replacement packs of 30 vials will be provided at visits as required, to a maximum of 3 packs x 30 vials.

Each pack will provide enough study drug for 28 days treatment (with 2 days of study drug overage to allow for the drug spilling or spoiling, and to provide a +/- 2 day window around study visits).

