9.5 Study Drug Administration

After giving consent and being recruited on to the study, the patient's baseline assessment will be carried out and recorded.

The first subcutaneous injection of ARA 290 at a dose of 4 mg will be self-administered by the patient at the first patient visit. The patient will receive practical instructions on how to self-administer the drug. The patient will be required to remain at the site for one hour after the first administration for observation. Any adverse events will be recorded in the CRF. The patient will self-administer subsequent 4 mg subcutaneous injections for the 84 day study drug period unless there is reason for discontinuation of the study drug.

Study medications should be injected subcutaneously in the front or side of the thigh daily, in the morning. Patients are advised to rotate daily injection sites to avoid injecting into the same area repeatedly. In the unlikely event that the patient is unable to inject into the thigh they may inject into the abdomen.

The patient will be provided with Study Drug Administration Guidelines to instruct them how to reconstitute the study drug for injection and how to administer the injection. The patient will also be provided with a Study Drug Diary Card and will be instructed to note each daily study drug administered.

The PI or designee should confirm that all study drugs are administered as per protocol by checking the returned Study Drug Diary Card. Any anomalies in study drug used/unused will be queried with the patient and in the event that the patient has not administered study drug, this will be recorded as a protocol deviation in the CRF.

The completed Study Drug Diary Card should be filed alongside the patient CRF.

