9.6 Study Drug Termination

The study drug will be discontinued if any of the following conditions are met prior to the study drug treatment period of 12 weeks:

- 1. Patient or clinician request for withdrawal from the study.
- 2. Patients whose sight is determined as deteriorating to the point of a 10 letter drop in sight. The study drug will be stopped and the patient will be offered the current standard care treatment.

Whilst on the study enrolled participants, [i.e. patients with DMO and thick retinas (400 microns or more)] will be receiving the study drug rather than the current standard treatment (currently anti VEGF drugs in the NHS). Patients who wish to withdraw from the study, those in whom sight loss occurs during the duration of the study or those completing the study in who DMO persists, will be offered this standard care treatment.

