1. BACKGROUND AND DESIGN

The hypothesis tested is that ARA 290, when administered subcutaneously at 4mg on a daily basis for 12 weeks, due to its anti-inflammatory, anti-apoptotic and neuroprotective effects, will be of therapeutic value to patients with diabetes mellitus and diabetic macular oedema.

This will be an interventional, exploratory, investigator led, pilot study with the aim of determining if ARA 290 administered at a daily dose of 4mg subcutaneously for 12 weeks to patients with DM and severe DMO (central retinal subfield thickness measured with spectral domain optical coherence tomography of \geq 400 microns), will have a beneficial effect on improving BCVA, reducing central subfield thickness, increasing central retinal sensitivity and retinal perfusion, increasing tear production and improving quality of life with no adverse events. Data obtained in this pilot study will be used to inform future larger studies.

The primary objective is to determine whether ARA 290 has a beneficial effect on BCVA in people with DM and DMO.

The secondary objectives are to determine whether ARA 290 administered at a daily dose of 4mg subcutaneously for 12 weeks to patients with diabetes mellitus and DMO can improve vision (as determined by the % of participants with a \geq 10 and \geq 15 ETDRS letter gain), reduce central subfield thickness, increase central retinal sensitivity, increase tear production and improve retinal perfusion and quality of life with no deleterious side effects. The effects of ARA290 on the systemic and metabolic control of participants will be also evaluated in an exploratory manner.

ARA 290 antibodies will be determined as, if they were to develop in people undergoing this treatment they could have an impact on the potential subsequent response to it.

Inflammatory markers will be evaluated to investigate the potential anti-inflammatory effect of this treatment. Carbamylated albumin will be obtained as an additional measure of renal function and metabolic status and glycosylated albumin will be obtained as a confirmatory marker of glucose control.

This is a prospective, open label, interventional, single centre, investigator led, phase II study to examine the effect of ARA 290 on DMO in patients with type 1 or 2 diabetes and central retinal subfield thickness of \geq 400 microns.

The study intervention is a subcutaneous daily administration of ARA 290 in a dose of 4mg for 12 weeks

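### The SAP Table 2 footnote sets expected exposure at 120 doses over 120 days, but the regimen is once daily for 12 weeks, which is 84 doses over 84 days

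*SAP*

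**What the plan says.** SAP Appendix 1, Table 2 has a row for the number of doses administered, to be shown as mean ± SD. Its footnote states: "patients are expected to have received 120 doses over 120 days".

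The treatment period is given elsewhere as follows:

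- SAP section 1: "The study intervention is a subcutaneous daily administration of ARA 290 in a dose of 4mg for 12 weeks".
- Protocol section 3.3 describes this study as "prolonging the duration of treatment, from 28 days, as used in most previous studies, to 84 days".
- Protocol section 9.5 has the patient self-inject daily "for the 84 day study drug period unless there is reason for discontinuation of the study drug".
- Protocol section 9.6 lists stopping conditions that apply if "met prior to the study drug treatment period of 12 weeks".

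On supply, Protocol section 9.2 gives packs of 30 vials and says: "Each pack will provide enough study drug for 28 days treatment". The two spare vials cover spillage or spoilage and are also there "to provide a +/- 2 day window around study visits".

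SAP section 7.3 asks for the number of treatments administered and for treatment compliance.

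**The concern.** The footnote disagrees with four statements of the regimen that agree with one another, one of them in the SAP itself. Both of its numbers are affected, the doses and the days.

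Table 2 is a results table, and the footnote is the only benchmark printed beside the exposure row. If the shell is followed as written, the wrong benchmark goes into the final report. A reader who sets a mean near 84 against 120 would conclude that patients missed roughly three doses in ten when they may have missed none. Exposure deserves a correct label in this trial because, by the protocol's own account, it is the first to extend dosing from the 28 days used in most previous studies to 84 days.

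**Working it through.** **Inputs**

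| Quantity | Value | Source |
|---|---|---|
| Stated expected exposure | 120 doses over 120 days | SAP Appendix 1, Table 2 footnote |
| Dosing frequency | 1 per day | SAP 1; Protocol 9.5 |
| Treatment period | 12 weeks | SAP 1; Protocol 9.6 |
| Treatment period | 84 days | Protocol 3.3, 9.5 |
| Pack contents and cover | 30 vials, 28 treatment days | Protocol 9.2 |
| Dispensing window around visits | ± 2 days | Protocol 9.2 |
| Week 12 outcome window | ± 7 days | Protocol 6.1; SAP 2.1 |
| Adverse event reporting period | to 30 days after last dose | Protocol 13.7 |

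**Step 1. Expected doses.** Doses = doses per day × weeks × 7 = 1 × 12 × 7 = 84. The stated 120 is not reproduced.

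**Step 2. Look for a route to 120.**

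- Dosing tied to the actual visit date within ± 2 days: 84 − 2 = 82 to 84 + 2 = 86 doses.
- Dosing tied to the week 12 outcome window of ± 7 days: 84 − 7 = 77 to 84 + 7 = 91 doses.
- Week 16 visit: 16 × 7 = day 112. The schedules in both documents show assessments only at this visit, and SAP section 6 records that no patient needed it.
- End of adverse event reporting: 84 + 30 = day 114, with no dosing after the treatment period.
- Supply, with three packs in total (the natural reading of Protocol 9.2): 3 × 28 = 84 treatment days, or 3 × 30 = 90 vials.
- Supply, if the maximum of three counts replacement packs only: 1 + 3 = 4 packs, so 4 × 30 = 120 vials. Those packs cover 4 × 28 = 112 treatment days, because two vials in each are overage.

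Only the last route produces the number 120. It counts vials supplied, including spares, and not doses expected. It may be where the footnote came from, but the documents do not say so. The conclusion does not depend on how the pack limit is read.

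**Step 3. Size of the discrepancy.**

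- Excess: 120 − 84 = 36 doses; 36/84 = 0.43.
- Apparent exposure of a fully adherent patient against 120: 84/120 = 0.70.
- With the ± 2 day window: 82/120 = 0.68 to 86/120 = 0.72.
- With the ± 7 day window: 77/120 = 0.64 to 91/120 = 0.76.

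**The case against.** The best case on the other side accepts the contradiction and says it hardly matters. The row is a plain mean ± SD, which is the same under either footnote. The SAP defines no compliance percentage with 120 as its denominator, so the 70% is a reader's inference and not a programmed output. A reader who knows the 12-week regimen from SAP section 1 would see the slip. Missed doses are also captured separately: Protocol section 9.5 says that "in the event that the patient has not administered study drug, this will be recorded as a protocol deviation in the CRF", and Table 2 has its own row for study drug administration violations. All of this stands, and it is why the point is minor.

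Three narrower objections also have some force:

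- The ± 2 day range rests on an assumption. Protocol section 9.2 mentions that window to explain the spare vials, section 9.5 fixes the period at 84 days, and the outcome window is wider. The solid comparison is 84 against 120. The ranges show only that neither window closes the gap.
- The footnote is internally coherent, since 120 daily doses do take 120 days. The fault is inconsistency with the regimen and not a failed sum.
- SAP section 7.3 asks for compliance as n (%) and defines no dose-based percentage, so advice about a denominator applies only if such a figure is produced.

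None of these makes 120 the expected exposure.

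**Conclusion.** The concern holds. The expected exposure under the stated regimen is 84 doses over 84 days, and the footnote overstates it by 36 doses, or 43%. Set against 120, full adherence would look like 70%. That figure assumes a reader uses the footnote as the denominator and that dosing follows the nominal 84 days.

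Severity is minor. The harm is confined to how one descriptive row is read, and no efficacy, safety or protocol-deviation output changes. Confidence is high, because the four regimen statements agree and nothing in either document provides for dosing beyond 12 weeks.

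**What to change.** Change the Table 2 footnote to state that 84 doses over 84 days are expected. If a dose-based compliance figure is reported under SAP section 7.3, use 84 as the planned number.

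The cost is one line of table-shell wording, with no new data collection, programming or analysis.
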